3.6 Training of research assistants

Multiple research assistants with experience in collecting qualitative data in a health care setting will be recruited to work in pairs and trained for 2 days. The training will cover, study objectives and approach as well as an in-depth review of the consent and assent process and data collection tools. Research assistants will also take part in the pre-test of data collection tools at one of the health centres in Kampala City. Data from this phase will not be included in the final analysis. Research assistants will also be trained on the COVID-19 standard operating procedures and study risk management procedures.

3.7 Ethical considerations

Permission to carry out the study was already obtained Columbia University IRB in New York City under expedited review for meeting the following two criteria

a) Research involving materials (data, documents, records, or specimens) that have been collected, or will be collected solely for non-research purposes (such as medical treatment or diagnoses).

b) Research on individual or group characteristics or behavior or research employing survey, interview, oral history, focus group, program evaluation, human factors evaluation, or quality assurance methodology.

We sought approval for the study through the IRB at Columbia University as part of our research team is located within that institution. We are seeking approval through SOMREC as the other researchers and research participants are located in Kampala, Uganda.

Page 25 of 142

3.8 Dissemination

The findings of this study shall be availed to the Kampala Capital City Authority, the Columbia Department of Pediatrics and Child Health, and all other stakeholders.

Risks / Benefits to Subjects

This is a minimal risk study. Some caregivers might find there are interview questions they do not want to answer; they can skip any questions they like and can stop the interview at any time. Interviews can be converted to be conducted online to decrease risk of COVID-19 transmission if necessary. Patients do not receive any care as part of the study they or their parent/caergiver only receive a text message. They can choose to act or not act on the message. The vaccination is not directly part of the intervention. Some parents might find the alerts to be intrusive, but we will design them based on parental input. In addition, they can opt out at any time. There is also a minimal risk of loss of confidentiality. However, we will assure confidentiality as below.

Compensation

Staff, caregivers, and adolescents taking part in interviews will receive Ugandan Shillings (UgX) 30,000 which is equivalent to ~USD\$8, officials taking part in interviews will receive UgX 75,000 which is equivalent to ~USD\$18. Families who were contacted over the phone about the study and traveled to the study-affiliated health centre to be consented and participate in interviews will be given travel compensation of UgX 10,000 which is the equivalent of ~USD\$3. Those enrolling in the pilot trial will receive Ugandan Shillings (UgX) 15,000 which is equivalent to ~USD\$4. These compensation amounts were determined by our Ugandan investigators based on what is customary.

Informed Consent

We have outlined above procedures to obtain written informed consent and assent.

Confidentiality Assurances

Data will be audio recorded using a device such as an audio recorder or smartphone. All data collection will occur in Uganda. Only participant first or last names will be recorded (last names will be used when it would be culturally or otherwise inappropriate for an interviewer to address an interviewee by their first name). Data will be stored on an encrypted computers and/or servers and in locked research offices at Makerere University and/or Global Health Uganda (the subcontractor). Only Columbia and Ugandan research staff will have access to the recordings. The researchers will be responsible for ensuring that the confidentiality of the data is maintained at all times. Paper documents will be stored in a locked cabinet at Makerere University and/or Global Health Uganda. The study database will reside at Columbia on the RedCap server. The recordings will be used solely for research purposes to inform the content of the intervention and possible future publications. The recordings will be destroyed upon conclusion of the study.

Conflict of Interest

There are no conflicts of interests amongst any of the researchers

Collaborative Agreements

None

Intended Use of Results

The intended use of the results is to design a trial of text message vaccine reminders, which if successful could lead to a larger-scale text message reminder program on timely human papillomavirus (HPV) vaccination in Ugandan adolescents. In addition, we will potentially publish a manuscript related to this data. The data will be used for future grant applications.

Storage of and access to research data by other users

All the data including informed consent forms should be kept at by the PI for at least 5 years before destruction.

Data Sharing

We will register the clinical trial component of this project with U.S. Clinicaltrials.gov in accordance of all reporting requirements, with an expectation that the Clinicaltrials.gov registration will occur prior to enrollment of the first subject in the clinical trial. All results and findings will be disseminated through professional scientific conferences, peer-reviewed publications including the final text messages, and reporting on Clinicaltrials.gov.

Both institutions will have a de-identified copy of the final analytic trial dataset. In addition, we will permit access to the data on the basis of the experience and scientific qualifications of the investigator(s) and their agreement to not reproduce or share the data with others and to not attempt to determine the identities of patients or locations. Requests must be submitted in writing on the letterhead of the sponsoring institution at which the research will be conducted and include identifying information about the Principal Investigator and Co-investigators, including their curricula vitae or NIH biosketch. This data set will be free of identifiers that would permit linkages to individual research participants or specific practice sites. Research data will be made available only if appropriate IRB permission are obtained. Data Use Agreements will be executed as necessary. Data will be able to be exported to common statistical packages (SPSS, SAS, Stata, R) for analysis.

Data Safety

This is a minimal risk study. Some caregivers might find there are interview questions they do not want to answer; they can skip any questions they like and can stop the interview at any time. There is also a minimal risk of loss of confidentiality. However, we will assure confidentiality. The researchers will be responsible for ensuring that the confidentiality of the data is maintained at all times. Paper documents will be stored in a locked cabinet at Makerere University and/or Global Health Uganda. The study database will reside at Columbia on a RedCap server. The recordings will be used solely for research purposes to inform the content of the intervention and possible future publications. The recordings will be destroyed upon conclusion of the study.

Data will be stored on an encrypted computers and/or servers and in locked research offices at Makerere University and/or Global Health Uganda (the subcontractor).

Study timeline											
Study Activity	Time in Months										
	1-4	5	6	7-10	8-16	17-19	20-24				
Proposal preparation	Х										

Study timeline

Hire and train study staff	Х						
Data collection		Х					
Transcription		Х					
Develop messages reminders			Х				
Pre-test reminder messages			Х				
AIM 3: Pilot RCT Enrollment and				Х			
Randomization							
Outcome observation					Х		
Process evaluation, analysis, stakeholder						Х	
presentations, R33 transition package							
preparation, manuscript preparation							

Statistical Analytic Plan v1.2

Official title: SEARCH: Short Message Service (SMS) Electronic Adolescent Reminders for Completion of HPV Vaccination - Uganda: Pilot

NCT number NCT05151367

Document dates 10/10/2022, 2/6/2023

Aim: To pilot assess the impact and feasibility of vaccine reminders on HPV vaccination

Primary Analysis

The outcome will be timeliness of vaccination (time to event). Time will be from start of main message series to receipt of the next needed dose. For those who did not receive the dose, time will be right censored at 6 months The primary analysis will be intention-to-treat (ITT), whether or not further messages were declined or undeliverable.

Timeliness of vaccine receipt will be compared using Kaplan-Meier curves using a stratified log rank test. In addition, in order to gain effect sizes needed for a future large-scale intervention, comparisons will also be stratified assessing those due for the first dose (initiation) and second dose (completion). It will also be assessed using chi square analyses.

A secondary per protocol analysis will only include those who received the entire set of reminders.

Outcome Variables

- 1) Receipt of by 24 weeks for dose 1 for uninitiated
 - a. Yes, if Day enrollment to HPV dose 1 is < 168 days
 - b. No, if Day enrollment to HPV dose 1 is >= 168 days
 - c. No, if never received
- 2) Receipt of by 24 weeks for dose 2 for initiated
 - a. Yes, if Day enrollment to HPV dose 2 is < 168 days
 - b. No, if Day enrollment to HPV dose 2 is >= 168 days
 - c. No, if never received
- 3) Receipt of by 24 weeks combined
 - d. Yes, if Day enrollment to next needed dose (1st or 2nd depending on if initiated or uninitiated) is < 168 days

- a. No, if Day enrollment to next needed dose (1st or 2nd depending on if initiated or uninitiated) is >= 168 days
- b. No, if never received

Analyses:

- 1. Chi square of randomization group by 24 week variables
- 2. Calculate relative "risk"
- 3. Check for interaction term by language and by site for randomization (separately)
- 4. Calculate number needed to treat for one additional vaccination by 24 weeks for dose 1, dose 2 or either (combined variable)
- 5. Run Kaplan-Meier curve. Outcomes are the 24 week variables.

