We will enroll only one child per family; if more than one is eligible, one will be randomly selected. For the pilot feasibility trial, we will enroll families of girls who are in need of either the first or second dose, with an outcome of receipt of next needed dose. Due to the need to complete the pilot feasibility trial quickly, we will only enroll those in need of the second dose if their next dose is due strictly between 8-20 weeks from enrollment. We will seek written consent from caregivers. We will seek written assent from adolescents of consented caregivers given instead. At enrollment, parents will be verbally administered a demographic and HPV vaccination knowledge and attitude survey.

After enrollment, the Ugandan project coordinator will randomize families into intervention vs. usual care arms (1:1 ratio) stratified by enrollment site, parental language (English or Luganda), and dose due (1st or 2nd) using a randomization module. Research staff will not know the study assignment during enrollment. The outcome assessor and analyst will remain blinded to arm assignments.

Families who report on the demographic survey their highest degree of schooling as P7 or below will be asked at enrollment if, in the case they are randomized to the intervention, they would prefer a voice reminder in lieu of texts; such reminders would include the same content, timing and interactivity as the texts. While in Kampala only 2.1% of women and 0.5% of men have no formal education, 17.6% of women and 17.1% of men completed only some primary school.31 Similarly, families whose daughter is returning to a boarding school and are enrolled at the Adolescent Clinic, health centres, or immunization post will be asked if, in the case they are randomized to the intervention, they want messages sent timed for the next school break. Alternatively, they can select the timing used for those not at boarding school. If the special timing is selected, we will account for the minimal interval between doses (for those in need of a second dose). Intervention-arm families enrolled through Child Days Plus will be sent their series prior to the next Child Days Plus event at their child's school or before any other special immunization day events, if the school holds one.

Intervention, Text Message Target, Content and Frequency:

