For those families randomized to the intervention arm: Based on our previous studies as well as the full country HPV vaccine evaluation highlighting the parents involvement as vaccine decision makers, we plan for the messages to be targeted to the parent, unless in Aim 1 families suggest that girls should also receive the message. All text messages are automated and will be sent in English or Luganda based on parental preference.

The message sequence consists of 5 weekly, main message reminders beginning 5 weeks before the

HPV vaccine dose due date, followed by a series of 2 primary booster messages.(Figure 3). This is based on our previous studies that showed that the median number of messages needed to come in for a vaccine was 5. If enrollment happens more than 4 weeks before the main messages are due to

start, engagement messages will be sent monthly until main messages start. The due date for the vaccine will depend on whether the first (initiation) or second

(completion) dose is due and the enrollment site.

For those who need to initiate vaccination and are:

- *Recruited as part of the school-based program*, the due date will be defined as the next Child Days Plus
- *Recruited in health centre and not in boarding school*, the due date will be defined as 5 weeks after message initiation
- *Recruited in health centre and are in boarding schools,* the due date will be the next school break
- *Recruited in the community*, the due date will be defined as the next HPV vaccination day at the community immunization post that is at least 5 weeks after message initiation

For those who need to complete the vaccination series and are:

- *Recruited as part of the school-based program*, the due date will be defined as the next Child Days Plus
- *Recruited in health centre and not in boarding school*, the due date will be defined as 6 months after the date of the first dose (which is the recommended interval between doses)
- *Recruited in health centre and are in boarding schools,* the due date will be the next school break that is a least 5 months after the date of the first dose, which is the minimal allowed interval between doses
- *Recruited in the community*, the due date will be defined as the next HPV vaccination day at the community immunization post that is at least 5 months after the date of the first dose

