Messages will focus on when/where to go for the next dose, and will include educational information identified in Aim 1. Messages will be different for those who need the first dose (initiation) and 2nd dose (completion). We will also include an interactive text message allowing participants to ask for and receive more information according to their specific needs, and receive an automated response with information on that subject. For those still unvaccinated, booster

messages will be sent bi-weekly for one month and then monthly until the end of the 6 month observation period for each individual during the pilot trial. Sites will be visited every 2-4 weeks to abstract data; we will stop messages for those already vaccinated. HPV registers for schools are generally kept with the affiliated KCCA health centre immunization nurses. For families of those unvaccinated who were first vaccinated at Child Days Plus will receive booster messages directing them to bring their daughter to the KCCA health centre affiliated with their school (who conducts their Child Days Plus outreach) as they will have missed the school vaccination day.

Usual Care arm: Families randomized to the *usual care arm* will not receive text message vaccine reminders.

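### The SAP's Kaplan-Meier clock runs 6 months from message start but its event counts 168 days from enrollment, so second-dose uptake comes out too low

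*SAP*

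**What the plan says.** **Clock.** SAP, Primary Analysis: "Time will be from start of main message series to receipt of the next needed dose".

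**Censoring.** The next sentence of the SAP: "For those who did not receive the dose, time will be right censored at 6 months". Neither document has a rule for a girl whose last register check came earlier.

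**Event.** SAP, Analyses, item 5: "Run Kaplan-Meier curve. Outcomes are the 24 week variables". Under Outcome Variables, each of those variables is Yes only if fewer than 168 days pass from enrollment to the dose.

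**Enrollment to message start.** Protocol 3.5.3 says of second-dose girls that "we will only enroll those in need of the second dose if their next dose is due strictly between 8-20 weeks from enrollment". The same section times the messages relative to that due date: "The message sequence consists of 5 weekly, main message reminders beginning 5 weeks before the" due date.

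**Follow-up.** Protocol 3.5.3 continues booster messages "until the end of the 6 month observation period for each individual during the pilot trial", without saying when that period begins. The Study timeline table places enrollment in months 7-10 and "Outcome observation" in months 8-16.

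**The concern.** The curve's time axis and its event have different origins (message start and enrollment) and different lengths (6 months and 24 weeks). A girl can receive her dose, have it recorded, and be within 6 months of message start, yet still count as a non-event because day 168 from enrollment has passed. The longer her wait for messages, the more of her clock is closed to events.

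Separately, giving every unvaccinated girl a full 6 months is right only if the registers were checked for that long. If they were not, unobserved time enters as event-free time.

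Both the protocol and the SAP say the dose-specific comparisons are meant to supply effect sizes for a later large trial. Uptake levels read off these curves would feed its event-rate assumptions.

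**Working it through.** The plan states no uptake assumption, so there is no figure of its own to reproduce here. Its sample size (154 girls, hazard ratio 1.67, 80% power) comes without an event rate.

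**1. Lag from enrollment to message start, second dose.** Due date 8 to 20 weeks after enrollment, messages 5 weeks before it: 8 − 5 = 3 weeks and 20 − 5 = 15 weeks. The limits are strict, so just under 15.

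**2. Part of the clock that can yield an event under item 5.** 168 days = 24 weeks from enrollment. After message start this leaves 24 − 3 = 21 down to 24 − 15 = 9 weeks, on a clock of 6 months = 26.09 weeks. Example: with a 15-week (105-day) lag, a dose on day 200 is day 200 − 105 = 95 on the clock, well inside 6 months, but is coded No.

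**3. Effect on uptake.** Assumptions: constant hazard; lag uniform on 3-15 weeks; girls coded No carried event-free to 6 months; control uptake p = 30.2%, borrowed from the adolescent-clinic 6-month completion figure in Protocol 2.0; treated uptake 1 − (1 − 0.302)^1.67 = 45.1%.

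- Weekly hazard λ = −ln(1 − p)/26.09: 0.01378 control, 0.02301 treated.
- Reported uptake = 1 − (e^(−9λ) − e^(−21λ))/(12λ).
- Control: 1 − (0.8834 − 0.7487)/0.1654 = 18.6%. Treated: 1 − (0.8129 − 0.6167)/0.2762 = 29.0%.

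| Control uptake assumed | True uptake | True difference | Reported under item 5 | Reported difference |
|---|---|---|---|---|
| 12% | 12.0% vs 19.2% | 7.2 points | 7.1% vs 11.5% | 4.4 points |
| 30.2% | 30.2% vs 45.1% | 14.9 points | 18.6% vs 29.0% | 10.4 points |
| 69.8% | 69.8% vs 86.5% | 16.7 points | 49.1% vs 67.2% | 18.1 points |

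Levels are too low in every row. The difference shrinks in the first two and widens slightly in the third.

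With no lag, the mismatch is only 26.09 − 24 = 2.09 weeks, and 30.2% becomes 1 − e^(−24 × 0.01378) = 28.2%.

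**4. Early uptake instead of constant hazard.** Protocol 3.5.3 cites a median of 5 messages, sent weekly. Suppose half of those vaccinated within 6 months come in by week 5, in both arms. An exponential shape truncated at 26.09 weeks then needs a rate of 0.1324 per week, and on average 87.6% of doses fall inside the 9-21 week windows. Reported uptake is 0.876 × 30.2% = 26.4% versus 0.876 × 45.1% = 39.5%, a difference of 13.1 points.

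**5. Events lost.** If all 154 girls needed the second dose (an upper bound; the mix is not stated) and hazards were constant, events fall from 77 × (0.302 + 0.451) = 58 to 77 × (0.186 + 0.290) = 37. If the log-rank test uses this coding, power Φ(ln 1.67 × √(events/4) − 1.96) falls from about 50% to about 34%. The hazard ratio itself hardly moves.

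**6. Censoring at 6 months, conditional on when follow-up stops.** Second-dose girls, assumptions as in step 3, true uptake 30.2% vs 45.1%:

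- Observation ends 6 months after enrollment: shortfall 3 to 15 weeks; reported 20.9% vs 32.3%.
- Observation ends at month 16, enrollment uniform over months 7-10: 52% of girls fall short, by 5.2 weeks on average; reported 27.5% vs 41.5%.
- Observation runs 6 months from message start with full abstraction: shortfall and bias are zero.

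In the first case, censoring at the true last observation removes the bias: at week 22 the control curve reads 26.2% (truth 26.2%), against 20.8% under the SAP rule. In 3,000 simulated trials of 77 per arm, the SAP censoring rule gave 4.8% type I error, a hazard ratio of 1.66 (1.66 with correct censoring) and power of 35.7% (35.6%).

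**The case against.** **Item 5 may be shorthand.** It could mean a separate curve timed from enrollment to 24 weeks, which would be self-consistent. But the SAP gives only one time origin for the Kaplan-Meier analysis, message start, and under this reading the primary curve would no longer be the one defined under Primary Analysis. The text needs settling either way.

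**Follow-up may be complete.** A reader might infer that the protocol's own follow-up ends up to 15 weeks before the 6-month censoring time. The documents do not establish this. Protocol 3.5.3 gives no start for the observation period, and it may be the same 6 months as the SAP's. The month-16 limit comes from a planning chart whose columns are hard to read in the available text, and it is not a data cut-off. Outcomes come from clinical registers, so a later abstraction can recover earlier doses, and no last abstraction date is stated. This objection stands, and the censoring point is therefore only conditional. It does not touch the item 5 conflict, which arises even with complete follow-up.

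**The size rests on a constant hazard.** This also stands. With early uptake the loss is much smaller (step 4).

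**The treatment comparison survives.** The hazard ratio and log-rank test are almost unaffected by the censoring rule. The relative risk and number needed to treat use the 168-day variables directly and do not depend on it.

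**Conclusion.** The item 5 conflict holds on the text: the Kaplan-Meier analysis has a clock and an event that do not match. For second-dose girls, reported 6-month uptake is too low in both arms: 18.6% vs 29.0% instead of 30.2% vs 45.1% under a constant hazard, or 26.4% vs 39.5% if uptake is early. At control uptake of 12% or 30.2% the absolute difference is also too small; at 69.8% it is slightly too large. These figures assume a uniform 3-15 week lag and that girls coded No are carried to 6 months. The SAP does not say what time a girl with a late dose receives.

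The censoring problem holds only if register follow-up stops before 6 months from message start. The timeline suggests this for late-enrolled second-dose girls, but the documents do not confirm it.

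A reader might also infer that the first- versus second-dose contrast is distorted. That is not shown. The 8-20 week limit covers second-dose girls only. First-dose girls recruited through schools wait for the next Child Days Plus, and first-dose boarders for the next school break, with no stated cap, so their lags may be as long or longer. First-dose health-centre girls not boarding need have no lag. Nor do the documents support reading this as a flaw that invalidates the randomised comparison.

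**What to change.** Change the SAP in three places and add one clarification to the protocol:

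1. **Item 5.** Make the Kaplan-Meier event receipt of the next needed dose, on the same clock and 6-month horizon as the primary analysis. Keep the 168-day variables for the chi-square test, relative risk and number needed to treat.
2. **Censoring.** Censor girls with no recorded dose at the earlier of 6 months (183 days) after clock start and the last register abstraction covering them.
3. **Clock start.** Define it in both arms as the scheduled message-start date, due date minus 5 weeks, computed identically for usual care, where no messages are sent. For first-dose health-centre girls not boarding, the due date is itself set from message initiation, so that date must be fixed by rule.
4. **Protocol 3.5.3.** State when the 6-month observation period begins.

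The cost is a few sentences. Sites are already visited every 2-4 weeks, so abstraction dates should be available and no new data collection is needed. The downside is fewer girls at risk late in the curve, hence wider intervals there.
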